5. ADVERSE EVENTS

5.1 DEFINITIONS

Adverse Event (AE): any untoward medical occurrence in a patient or clinical study subject.

Serious Adverse Event (SAE): any untoward and unexpected medical occurrence or effect that:

- Results in death
- Is life-threatening refers to an event in which the subject was at risk of death at the time of the event; it does not refer to an event which hypothetically might have caused death if it were more severe
- Requires hospitalisation, or prolongation of existing inpatients' hospitalisation
- Results in persistent or significant disability or incapacity
- Is a congenital anomaly or birth defect

Medical judgement should be exercised in deciding whether an AE is serious in other situations. Important AEs that are not immediately life-threatening or do not result in death or hospitalisation but may jeopardise the subject or may require intervention to prevent one of the other outcomes listed in the definition above, should also be considered serious.

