5.3 REPORTING PROCEDURES

All adverse events should be reported. Depending on the nature of the event the reporting procedures below should be followed. Any questions concerning adverse event reporting should be directed to the Chief Investigator in the first instance.

[figure not shown]

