5.3.1 Non serious AEs

All such events, whether expected or not, should be recorded.

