5.3.2 Serious AEs

An SAE form should be completed and faxed to the Chief Investigator within 24 hours. However, relapse and death due to mitral valve disease, and hospitalisations for elective treatment of a pre-existing condition do not need reporting as SAEs.

All SAEs should be reported to the <name of REC> where in the opinion of the Chief Investigator, the event was:

- 'related', ie resulted from the administration of any of the research procedures; and
- 'unexpected', ie an event that is not listed in the protocol as an expected occurrence

Reports of related and unexpected SAEs should be submitted within 15 days of the Chief Investigator becoming aware of the event, using the NRES SAE form for non-IMP studies. The Chief Investigator must also notify the Sponsor of all SAEs.

Local investigators should report any SAEs as required by their Local Research Ethics Committee, Sponsor and/or Research & Development Office.

Contact details for reporting SAEs [contact], attention [name] Please send SAE forms to: [name] [contact] (Mon to Fri 09.00 – 17.00)

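### The SAE definition in Protocol 5.1 includes unexpectedness, which conflicts with 5.3.2 and may leave serious but foreseeable events outside 24-hour and sponsor reporting

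*Protocol*

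**What the plan says.** Protocol section 5.1 defines an adverse event (AE) as "any untoward medical occurrence in a patient or clinical study subject", with no condition on expectedness. The SAE definition that follows adds one: "any untoward and unexpected medical occurrence or effect that" leads to death, threat to life, hospitalisation, lasting disability or congenital anomaly. A closing paragraph lets medical judgement add important AEs outside those criteria: those that "may jeopardise the subject or may require intervention to prevent one of the other outcomes listed in the definition above, should also be considered serious". That paragraph does not mention expectedness.

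Section 5.3 opens with a general rule, "All adverse events should be reported", and refers the reader to procedures that depend on the kind of event:

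- For events that are not serious, section 5.3.1 gives a single rule: "All such events, whether expected or not, should be recorded".
- For events that are serious, section 5.3.2 begins with a deadline: "An SAE form should be completed and faxed to the Chief Investigator within 24 hours". Two exemptions follow: "relapse and death due to mitral valve disease, and hospitalisations for elective treatment of a pre-existing condition do not need reporting as SAEs". The Chief Investigator must tell the sponsor of every SAE. An ethics committee report is due within 15 days for SAEs that the Chief Investigator considers both related to a research procedure and "unexpected', ie an event that is not listed in the protocol as an expected occurrence".

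The available text of the protocol lists no expected occurrences. The SAP does not deal with safety reporting.

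**The concern.** Seriousness describes the outcome of an event. Expectedness describes whether it was foreseen. Section 5.1 merges the two, and the 24-hour and sponsor steps in 5.3.2 depend on the merged definition. A reporter who takes 5.1 at its word can decide that a grave complication was foreseeable, conclude that it is not an SAE, and send no form. The Chief Investigator, whose opinion on relatedness and expectedness 5.3.2 relies on, might then not be told within 24 hours.

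This matters in a surgical cohort. The research procedures in Protocol section 3 include biopsies of both ventricles during open-heart surgery, and exercise testing that continues until the patient must stop or reaches predicted maximum heart rate. The few patients who have not already had a right heart catheterisation are referred for one. Serious harm from such procedures can resemble recognised complications of the surgery itself, so these events are among the easiest to label as expected.

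**Working it through.** No arithmetic applies. The claim depends on no rate, sample size or error level, and the documents give no figure to reproduce. The check sets the 5.1 definition against each reporting step.

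**Step 1. Route each kind of event under two readings.** Reading A takes the 5.1 definition literally. Reading B tests expectedness only where 5.3.2 does. Both are subject to the exemptions named in 5.3.2.

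| Event | Reading A | Reading B |
|---|---|---|
| Meets a listed criterion, unexpected | SAE: 24-hour form and sponsor notice; ethics committee if also related | Same |
| Meets a listed criterion, foreseeable | Not an SAE under the main definition: no 24-hour form or sponsor notice; only the general rule in 5.3 applies | SAE: 24-hour form and sponsor notice; expectedness affects only the ethics committee report |
| Important AE outside the listed criteria, foreseeable or not | Can be considered serious through the judgement paragraph | Same |

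The readings differ only in the second row. Reading A also gives an odd ordering: a lesser foreseeable event can enter the SAE route through medical judgement, while a graver one that meets a listed criterion may not.

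**Step 2. Look for a route for the second row under Reading A.** Section 5.3.1 does include expected events, but its heading limits it to non-serious AEs, and a life-threatening event does not fit there. Section 5.3.2 covers serious events but relies on the 5.1 definition. The event falls between the two. The general rule in 5.3 still requires a report, but sets no deadline and no sponsor step of its own.

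**Step 3. Ask which reading the rest of section 5 supports.**

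- The second expectedness test in 5.3.2 would be redundant if every SAE were already unexpected.
- The named exemptions would be largely unnecessary if foreseeable events were already excluded. Complications of surgery or of the research procedures are not among them.
- The only definition of *unexpected* in the protocol is the one in 5.3.2, which refers to a list. The available text has no list, so on that definition no event would count as expected.

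All three favour Reading B. But the 5.3.2 definition is given for the ethics committee test. Section 5.1 uses the word without defining it or pointing forward, so the same event can be routed in opposite ways depending on which section the reporter follows.

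**Limit of the check.** The figure in section 5.3 could not be seen, and nothing is inferred from that. If it shows reporting routes, it should be checked against the text.

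**The case against.** The strongest reply is that section 5, read as a whole, already leads to the right result. If the 5.3.2 definition of *unexpected* is carried back to 5.1, the missing list means that every event is unexpected, so every event meeting a criterion is an SAE. The judgement paragraph admits important AEs whatever their expectedness, the general rule covers all AEs, and the sponsor hears of all SAEs. Reporters would probably follow this ordinary reading.

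Much of that stands, and it limits the point. A reader might infer from 5.1 that foreseeable serious harms can never reach the 24-hour and sponsor route. The documents do not support that: the judgement paragraph has no expectedness condition, and the only stated test of expectedness excludes nothing in the available text. A reader might also infer that such events are handled merely as non-serious AEs. That is not supported either, because 5.3.1 is confined to non-serious events.

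The reply does not remove the contradiction. Carrying the 5.3.2 definition back to 5.1 is an inference the protocol never states. The judgement paragraph is written for events below the listed criteria; it does not clearly restore foreseeable events that meet them. The sponsor rule uses the same SAE definition and so inherits its ambiguity. That the word in 5.1 looks like a drafting slip is a reason to correct it; site staff should not have to work out that part of a governing definition is to be ignored.

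**Conclusion.** The point holds as an inconsistency between Protocol sections 5.1 and 5.3.2. On the literal wording of 5.1, a serious but foreseeable event that meets a listed criterion may fall outside the 24-hour form and sponsor notification, with no clear alternative route. The surrounding text suggests that this was not intended.

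The size cannot be stated. The documents give no rate of serious events and no indication of how often reporters would apply the literal reading. The definition covers all 50 planned patients. No outcome or analysis in the SAP is affected; the consequence is confined to safety oversight.

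The conclusion assumes that some reporters will follow 5.1 as written, and that the unseen figure in section 5.3 does not resolve the conflict. The correction is worth making because it is cheap and the events at risk of omission are serious ones.

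**What to change.** Delete the two words that require unexpectedness from the SAE definition in Protocol section 5.1, so that it turns on the listed seriousness criteria alone. Keep expectedness solely as the 5.3.2 test for ethics committee reporting. The 24-hour form and sponsor notification would then apply to all serious events other than those 5.3.2 already exempts.

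The cost is a protocol wording change and some extra SAE forms among about 50 surgical patients.

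A list of expected events is not needed for this correction. With no list, every related SAE counts as unexpected and goes to the ethics committee within 15 days. Listing foreseeable harms of biopsy, exercise testing or catheterisation would take those events out of that report.

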5.3 REPORTING PROCEDURES

All adverse events should be reported. Depending on the nature of the event the reporting procedures below should be followed. Any questions concerning adverse event reporting should be directed to the Chief Investigator in the first instance.

[figure not shown]
5.3.1 Non serious AEs

All such events, whether expected or not, should be recorded.

5.3.2 Serious AEs

An SAE form should be completed and faxed to the Chief Investigator within 24 hours. However, relapse and death due to mitral valve disease, and hospitalisations for elective treatment of a pre-existing condition do not need reporting as SAEs.

All SAEs should be reported to the <name of REC> where in the opinion of the Chief Investigator, the event was:

- 'related', ie resulted from the administration of any of the research procedures; and
- 'unexpected', ie an event that is not listed in the protocol as an expected occurrence

Reports of related and unexpected SAEs should be submitted within 15 days of the Chief Investigator becoming aware of the event, using the NRES SAE form for non-IMP studies. The Chief Investigator must also notify the Sponsor of all SAEs.

Local investigators should report any SAEs as required by their Local Research Ethics Committee, Sponsor and/or Research & Development Office.

Contact details for reporting SAEs [contact], attention [name] Please send SAE forms to: [name] [contact] (Mon to Fri 09.00 – 17.00)

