At the other end of the clinical spectrum, the increased operative mortality and worse long term prognosis of symptomatic patients is well proven. Patients with New York Heart Association Class III or IV status have excessive operative mortality and significantly increased mortality at 10 years (7). Both this study and another (8) have demonstrated that preoperative ejection fraction is an independent predictor of long term survival. Although this evidence base does not support prophylactic surgery on asymptomatic patients, it does highlight the importance of avoiding the long term sequelae of MR in causing symptomatic status or left ventricular impairment. Hence attention has turned to objective markers or investigations independent of symptomatic status that may be subjectively assessed in the early phases; to help identify patients who would prognostically benefit from earlier surgical intervention.

As a result of rheumatic fever being the most common etiology, mitral stenosis (MS) is the least common valvular lesion in the hospital population (2) and has a low prevalence rate in epidemiological studies (1) in industrialized countries. However, it still causes significant morbidity and mortality worldwide. The preferred treatment for severe mitral stenosis in those patients with favourable valvular anatomy is percutaneous mitral commissurotomy. In one single centre follow up, there was a low immediate risk of the procedure with 89% of patients obtaining good immediate results defined as a final mitral valve area greater than 1.5cm² without significant mitral regurgitation and a 20 year rate of good functional results of 30.2% (9).

[name] 22/12/16 16:42 Deleted: 2 [name] 22/12/16 16:43 Deleted: 1 [name] 22/12/16 16:43 Deleted: 9

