Version 3, 31/12/2016 However, in those patients with unfavourable valvular anatomy; there are no randomised trials to guide the best timing of surgery. Survival benefit increases with more advanced symptoms, but surgical risk increases with pulmonary hypertension so it has been suggested to intervene when symptoms are more than mild, but before the development of pulmonary hypertension (10). An area of uncertainty exists in asymptomatic patients with severe MS or those with symptoms out of proportion with the severity of MS. Current guidelines suggest the use of stress echocardiography and intervention if the mean transmitral pressure gradient is greater than 15mmHg during exercise or peak pulmonary artery systolic pressure exceeds 60mmHg (11). However, this guidelines is based on level C evidence and there is no data comparing these parameters with objective measurements of exercise capacity and its relationship with operative risk or long term prognosis.

In summary, severe mitral valve disease is a common valvular pathology that causes a significant burden of disease in the United Kingdom and worldwide. Current guidelines for timing of operative intervention are mostly based on expert opinion rather than randomised trials or studies. There is currently no proven prognostic benefit from surgery on asymptomatic patients. Patients with significant symptoms benefit from surgery, but have worse long term prognosis than the general population. It is difficult to assess early or mild symptoms and there is no significant evidence base objectively measuring exercise capacity and its correlation with quality of life and markers of cardiac or respiratory function before and after surgery.

Pathophysiology of severe mitral valve disease

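### Protocol section 5.3.2 exempts deaths attributed to mitral valve disease from SAE reporting, so an ambiguous post-operative death can go without any recorded judgement on the research biopsy

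*Protocol*

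**What the plan says.** Protocol section 5.1 defines an SAE as "any untoward and unexpected medical occurrence or effect that" meets one of a list of criteria, of which death is the first. Its closing paragraph adds that other important events "should also be considered serious".

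Section 5.3 asks for every adverse event to be reported, by whichever of the procedures that follow fits the event, and refers questions to the Chief Investigator. Section 5.3.1 covers the recording of non-serious events.

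Section 5.3.2 requires an SAE form to reach the Chief Investigator within 24 hours, and then makes an exception: "relapse and death due to mitral valve disease, and hospitalisations for elective treatment of a pre-existing condition do not need reporting as SAEs". SAEs go to the ethics committee within 15 days if the Chief Investigator considers that two conditions are met. The event must be related, meaning that it "resulted from the administration of any of the research procedures". It must also be unexpected, which the section explains as "ie an event that is not listed in the protocol as an expected occurrence". It also states: "The Chief Investigator must also notify the Sponsor of all SAEs".

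Section 4.2 makes surgery for severe mitral valve disease the entry condition. Section 3 (Intra-operative specimens) plans left and right ventricular samples during that operation. Section 4.3 leaves out of the biopsy element those patients in whom adequate samples cannot be obtained.

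**The concern.** The exempted cause of death is the one disease that every participant has. An exemption of this kind can suit a study with no invasive research procedure. Here the study adds sampling of both ventricles, on the diseased organ and during the operation for that disease. Whether the biopsy played a part is the question that safety reporting should ask after a death. Under section 5.3.2 that question is reached only if the death has not already been assigned to the disease, so an earlier opinion on cause decides whether cause is examined.

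What is at stake is patient-safety oversight of an added research procedure. In the readable text, SAE reporting to the Chief Investigator, Sponsor and ethics committee is the only route described for that oversight. The SAP describes no adverse-event analysis, and no planned correlation, comparison or regression estimate depends on this point.

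**Working it through.** The plan gives no death rate or biopsy complication rate, so there is no figure of its own to reproduce. The check is mainly a reading of the sections together.

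**1. Who is covered by the exempted cause.** The planned population is 50 (Study Summary), and all must have severe mitral valve disease (section 4.2). That is 50 of 50.

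**2. Who has the research procedure.** Biopsy of both ventricles is the plan for all (section 3), less those in whom adequate samples cannot be taken (section 4.3). The number biopsied is therefore at most 50.

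**3. What depends on SAE status.** In section 5.3.2 three steps apply to SAEs: the form to the Chief Investigator, the related-and-unexpected judgement that leads to an ethics-committee report, and the notice to the Sponsor. The readable text asks about relatedness to research procedures nowhere else.

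**4. Three deaths traced through the text.**

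| Death after surgery | Exempt? | Relatedness judged? | Sponsor told? |
|---|---|---|---|
| Clearly caused by the biopsy | No | Yes | Yes |
| Clearly caused by the operation | No | Yes | Yes |
| Cause uncertain, attributed to mitral valve disease | Yes | Not required | Not required |

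Only the third row is a gap. The readable text does not say who makes the attribution, sets no peri-operative limit on the exemption, and requires no check on the biopsy before the exemption is used.

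**5. Whether the general rule closes the gap.** Section 5.3 wants all adverse events reported, so such a death may still be logged. But the section defers to the procedures beneath it. Section 5.3.1 deals with non-serious events, and section 5.3.2 exempts these deaths. No relatedness judgement follows. The rule narrows the gap without closing it.

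**6. Whether an ambiguous attribution is plausible.** Section 1.1 says of mitral regurgitation that "the increased operative mortality and worse long term prognosis of symptomatic patients is well proven", and of mitral stenosis that "surgical risk increases with pulmonary hypertension". Operative risk and stage of disease are thus linked in the protocol's own account. That a doctor might put a post-operative death in a sicker patient down to the disease is an inference from this, not a statement in the documents.

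**7. Size.** Let N = 50 and let m be post-operative mortality, assumed to be 1% to 5%. Expected deaths = N × m:

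- 50 × 0.01 = 0.5
- 50 × 0.05 = 2.5

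The gap is these deaths multiplied by the share that are in biopsied patients, of uncertain cause and attributed to the disease. That share lies between 0 and 1 and is not given, so 0.5 to 2.5 is a ceiling and not an estimate.

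**8. The word *unexpected* in section 5.1.** Section 5.3.2 defines it as not listed in the protocol as expected. The readable text lists no expected occurrences, so on the protocol's own definition the word removes no events from the SAE definition.

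**The case against.** The strongest reply is that the protocol already asks for all adverse events to be reported, sends doubtful cases to the Chief Investigator, and exempts only deaths due to the disease. Deaths from surgery or biopsy are untouched. The background statements concern operative mortality and surgical risk, and neither says that such deaths would be classed as due to the valve disease. A figure in section 5.3 is also not readable and might set out further steps.

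Much of this stands. It confines the point to deaths of uncertain cause, makes their frequency unknowable from the documents, and means that statements about what is absent hold only for the readable text. It does not remove the point. Reporting an event as an adverse event carries no duty to judge relatedness, and the exemption sentence stands whatever the figure shows.

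A reader might infer two stronger things. One is that every post-operative death escapes reporting. The wording does not support that, because only deaths attributed to the disease are exempt. The other is that requiring an SAE to be unexpected drops the recognised complications of heart surgery. That needs an ordinary clinical meaning in place of the definition in section 5.3.2. On that definition nothing is lost, so no count of missed complications is justified.

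**Conclusion.** The concern holds in a narrow form. As written, section 5.3.2 allows a post-operative death of ambiguous cause, once attributed to mitral valve disease, to pass without an SAE form, notice to the Sponsor, or a recorded judgement on whether the ventricular biopsy contributed. This is a stated rule that weakens safety oversight, not merely missing detail. The conclusion rests on the readable text and on the inference that some such deaths could reasonably be attributed to the disease. Few events are in question, fewer than the 0.5 to 2.5 total unless every death met all the conditions, but each would be of the most serious kind. The change should be made because it is cheap and bears on patient safety.

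**What to change.** In section 5.3.2, remove death from the exemption and leave the rest of that sentence as it is. Then add: *All deaths are reported as SAEs whatever the presumed cause, and for any participant who had a ventricular biopsy the Chief Investigator records whether the biopsy contributed.*

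The cost is one wording change, one relatedness entry on the form, and extra SAE forms for at most the number of deaths calculated above. Attributing cause after open-heart surgery will remain a matter of judgement; the change ensures that the judgement is made and recorded. It needs no extra patients, visits, procedures or analyses.

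An optional tidy-up, with no demonstrated effect, is to delete the requirement of unexpectedness from the SAE definition in section 5.1, since section 5.3.2 already applies it as a separate test for ethics-committee reporting.
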